Study Protocol

With the approval of the XXXXXX Clinical Research Ethics Committee dated 26.12.2023 (No. 2023-172) and registration on ClinicalTrials.gov (NCT06241794), this study commenced. The study was conducted as a prospective, randomized, and blinded trial in the operating rooms of XXXXXXXXX Hospital between 01.01.2024 and 01.05.2024. A total of 72 patients, aged 18-65, classified as ASA (American Society of Anesthesiologists) physical status I-II, who were scheduled for laparoscopic cholecystectomy by the general surgery clinic, were included in the study after obtaining written and verbal consent. The study was designed and conducted in accordance with the ethical principles set forth in the Declaration of Helsinki.

Patient randomization was performed using an internet-based software program (Research Randomizer, http://www.randomizer.org/). Patients were randomly assigned to two groups based on the type of nerve block performed:

- Group 1 (n=35): Patients who received a modified thoracoabdominal nerve block via a perichondrial approach (M-TAPA)

- Group 2 (n=37): Patients who received a serratus intercostal plane block combined with a rectus sheath block (SIPB + RSB)

Inclusion criteria:

- Scheduled for laparoscopic cholecystectomy due to cholelithiasis
- ASA physical classification I-II
- Age between 18-65 years
- Body mass index (BMI) <35
- Patients who read and accepted the informed consent form

Exclusion criteria:

- Patients unwilling to participate
- ASA physical classification III or higher
- BMI >35
- Patients unable to score pain using the NRS system

- Patients with allergies to the local anesthetic and analgesic drug used
- Pregnant and breastfeeding patients
- Patients under 18 or over 65 years of age
- Patients with uncontrolled anxiety
- Patients with alcohol and drug addiction
- Patients with neuromuscular diseases and peripheral nerve disorders
- Patients with widespread chronic pain
- Patients with hepatic and renal failure
- Patients with contraindications for peripheral block
- Patients undergoing a second procedure along with laparoscopic cholecystectomy
- Patients with a history of abdominal surgery or trauma
- Patients where laparoscopic surgery was converted to open surgery
- Patients with technical issues using patient-controlled analgesia (PCA) devices
- Patients unable to understand or complete the Quality of Recovery-15 (QoR-15) scale

All necessary information regarding the procedures was provided to the randomized patients, and their written consent was obtained. Patients' ASA status and demographic characteristics (gender, age, height, weight, BMI, chronic diseases) were recorded. Surgeons and postoperative follow-up healthcare workers were not informed of the group assignments, maintaining blinding in the study. Preoperative QoR-15 questionnaires were completed before patients were taken to the operating room. Standard anesthesia monitoring (non-invasive arterial blood pressure measurement, heart rate, electrocardiography, peripheral oxygen saturation measurement) was applied to all patients. A 20G catheter was used to establish a peripheral venous line. The induction of anesthesia was recorded. For premedication, 0.03 mg/kg iv midazolam (Sedozolam, Monemfarma, Istanbul) was administered, and after preoxygenation, anesthesia was induced with 2 mg/kg propofol (Propofol-PF, Polifarma, Tekirdağ) and 1 mcg/kg fentanyl (Fentanyl-PF, Polifarma, Tekirdağ). After administering 0.6 mg/kg iv rocuronium bromide (Jecron, Tüm Ekip İlaç, Istanbul) and achieving muscle relaxation, endotracheal intubation was performed. Mechanical ventilation was provided in pressure

controlled mode targeting an end-tidal CO2 value of 35-40 mmHg. Anesthesia was maintained with an O2/air mixture (FiO2: 0.40), sevoflurane (Sevorane, AbbVie, Italy) (minimum alveolar concentration 0.8-1), and iv remifentanil (Ultan, Centurion Pharma, Ankara) infusion. The remifentanil infusion was adjusted in the range of 0.01-0.2 mcg/kg/min to keep the patient's mean arterial blood pressure within 20% of the baseline value. The start time of surgery was recorded. In all laparoscopic cholecystectomy operations, standard 4 trocar sites (umbilicus, epigastric region below the xiphoid, and subcostal area within the right midclavicular and right anterior axillary lines) were used. The operation was performed with the patient in the supine position and 30° reverse Trendelenburg position. Pneumoperitoneum was maintained with CO2 insufflation at an intraperitoneal pressure of 12 mmHg. The patient's intraoperative vital signs were monitored according to routine anesthesia protocol.

Thirty minutes before the end of the surgery, all patients received 1 g iv paracetamol (Partemol, Vem ilaç, Tekirdağ), 1 mg/kg tramadol (Tramosel, Haver farma ilaç, Turkey), and 4 mg ondansetron (Laufran, Haver pharma, Tekirdağ). After the completion of the surgery, all block procedures were performed under sterile conditions while the patient was supine under anesthesia. The end time of surgery, end time of anesthesia, time of block performance, and duration from block performance to the end of anesthesia were recorded. All blocks were performed under aseptic conditions.

For the M-TAPA block, USG (Logiq V2, GE, USA) guidance was used to identify the transversus abdominis, internal oblique, and external oblique muscles at the level of the 10th rib in the sagittal plane at the costochondral angle with a linear probe. The probe was angled deeply at the costochondral angle adjacent to the 10th rib to visualize the costal cartilage's inferior surface at the midline. Using an in-plane technique, a 22-G, 80-100 mm block needle (B Braun Stimuplex Ultra, 22 G, 80 mm, Germany) was advanced cranially, directing the needle tip towards the posterior surface of the 10th costal cartilage below the chondrium. Twenty milliliters of 0.25% bupivacaine (Buvasin, VEM ilaç, Turkey, prepared by diluting 10 mL 0.5% with 10 mL saline) was injected under the chondrium. The same procedure was performed on the opposite side.

For SIPB, USG guidance identified the serratus anterior and intercostal muscles at the 8th rib level along the right mid-axillary line. A 22-G, 80 mm block needle was used to inject 20 mL of 0.25% bupivacaine between these muscles. SIPB was performed only on the right side.

For RSB, USG guidance placed a linear probe transversely just above the umbilicus and slightly lateral to the midline. After visualizing the rectus abdominis muscle, posterior rectus sheath, and the hypo-echoic space between them, a 22-G, 80 mm block needle was advanced in-plane through the subcutaneous tissue until the needle tip reached the space between the rectus abdominis muscle's epimysium and the posterior rectus sheath. After negative aspiration, 10 mL of 0.25% bupivacaine was injected. Adequate spread was confirmed by lifting the epimysium of the rectus abdominis muscle while depressing the posterior fascia and peritoneum. The same procedure was performed on the opposite side.

Following the completion of the block procedures, neuromuscular blockade was reversed with 4 mg/kg sugammadex (Brimadex, Polifarma ilaç, Tekirdağ) under 80% O2 ventilation. Patients with adequate spontaneous respiration were extubated and transferred to the recovery room. Patients' vital signs, pain scores, and postoperative nausea and vomiting (PONV) scale were monitored in the recovery room. Pain assessment using the numerical rating scale (NRS) was performed at rest (static) and during active movement (transitioning from lying to sitting - dynamic). Pain intensity was rated from 0 (no pain) to 10 (worst imaginable pain). For postoperative analgesia, iv tramadol PCA was administered. The PCA protocol was set to 10 mg bolus tramadol on demand with a 20-minute lockout period without basal infusion. Tramadol consumption was recorded at 0-1 hour, 0-12 hours, 12-24 hours, and the total at 24 hours. Patients with a pain score above 4 in the recovery room received 25 mcg iv fentanyl as rescue analgesia, which was recorded.

Patients with an Aldrete score of 9 or higher were transferred to the ward. Postoperative pain follow-up was conducted by an anesthetist blinded to the group assignment. NRS scores were recorded at 0, 1, 3, 6, 12, 18, and 24 hours postoperatively. All patients received 1 g iv paracetamol every 8 hours for postoperative analgesia. Patients with pain scores above 4 despite the analgesic regimen received 50 mg iv dexketoprofen (Ketavel, Deva İlaç, Kocaeli) as rescue analgesia.

To determine the sensory block's dermatomal level, pinprick testing was performed at 2 and 24 hours postoperatively using a sterile needle along a vertical line 3-5 cm away from the midline and mid-axillary line between the T3-L1 sensory levels. A three-point numerical scale (0 = no prick sensation, 1 = reduced prick sensation, 2 = normal prick sensation) was used. Scores of 0 or 1 were considered effective. Normal sensation in the shoulder was used for comparison.

Patients were monitored for PONV within the first 24 hours postoperatively using a scale (PONV 1: no nausea or vomiting, PONV 2: nausea but no vomiting, PONV 3: single episode of vomiting or persistent nausea, PONV 4: two or more episodes of vomiting or severe/persistent retching). Patients with a PONV score of 2 or higher received 4 mg iv ondansetron. The total ondansetron dose administered within the first 24 hours postoperatively was recorded.

Patients completed the QoR-15 (Quality of Recovery-15) questionnaire, a self-report measure of postoperative recovery quality, twice: once in the waiting area on the morning of surgery and again 24 hours postoperatively. The time to first oral intake, time to first flatus/stool, and time to first mobilization (standing unaided) within the first 24 hours postoperatively were recorded.

Statistical Methods

The statistical analyses of the data obtained in this thesis were performed using the SPSS software package (Version 22.0, SPSS Inc., Chicago, IL, USA - Licensed by Hitit University). Descriptive statistics were presented as mean \pm standard deviation for continuous data showing normal distribution, median (min-max) for continuous data not showing normal distribution, and number and percentage (%) for categorical data. The normality of the data distribution was analyzed using Shapiro-Wilk tests. To compare the means of two independent samples of continuous variables, the independent samples t-test was used for normally distributed data, and the Mann-Whitney U test was used for data not normally distributed. For comparisons of two dependent groups of continuous variables, the paired t-test was applied for normally distributed data. The Friedman test was used for comparing numerical variables among more than two dependent groups with data not normally distributed. After variance analysis, Bonferronicorrected post-hoc tests were applied to determine the source of differences among groups. Relationships between categorical variables for two independent groups were evaluated using the Chi-square test or Fisher exact test, depending on the cell counts in cross-tabulations. Statistical significance was set at p<0.05.

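### The PCA and QoR-15 exclusions have no time point and can remove whole patients after randomisation and block, with no analysis set or missing-data rule to limit this

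*Combined protocol and SAP*

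**What the plan says.** Two items in the Exclusion criteria of the Study Protocol matter here: "Patients with technical issues using patient-controlled analgesia (PCA) devices" and "Patients unable to understand or complete the Quality of Recovery-15 (QoR-15) scale". Both exclude the patient rather than a measurement, and neither says when it applies. The same list holds an item that can be judged at screening, "Patients unable to score pain using the NRS system", and one that can only arise during the operation, "Patients where laparoscopic surgery was converted to open surgery". The list therefore mixes eligibility criteria with later events.

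The protocol's order of events is:

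- **Allocation.** Patients are already called randomised before they reach the operating room: "All necessary information regarding the procedures was provided to the randomized patients, and their written consent was obtained".
- **Baseline questionnaire.** "Preoperative QoR-15 questionnaires were completed before patients were taken to the operating room".
- **Block.** Given once surgery is complete, with the patient still anaesthetised.
- **PCA.** On-demand tramadol after surgery, with no background infusion. Consumption is recorded for three intervals and as a 24-hour total.
- **Second QoR-15.** Completed 24 hours after surgery.

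On numbers, the protocol says that 72 patients "were included in the study after obtaining written and verbal consent" and gives groups of 35 and 37, each described by the block received. It gives no separate counts of patients randomised, excluded and analysed. Statistical Methods covers descriptive statistics, tests, a Bonferroni correction and the significance level. It says nothing about analysis sets, analysis by assigned arm or missing data.

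**The concern.** Randomisation protects the comparison only while patients stay in it regardless of what happens after allocation. Read as a device fault, the PCA item removes a randomised and treated patient for an event that comes after both. Read against the 24-hour form, the QoR-15 item does the same, and the reason for removal may itself be an outcome: a patient too unwell to finish a recovery questionnaire may be one who recovered badly.

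The removal also goes further than the problem requires. A PCA fault leaves tramadol consumption unmeasurable, but pain scores, pinprick level, PONV, ondansetron use, QoR-15 and the recovery times can still be observed. An incomplete 24-hour questionnaire leaves only QoR-15 missing. Excluding the patient discards the rest, and the plan contains no rule that would keep it.

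**Working it through.** The plan states no sample-size calculation, dropout allowance or number of exclusions, so there is no design figure to reproduce. The one available check is 35 + 37 = 72, which agrees.

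**Timing of each exclusion**

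| Item | When it can arise | Can the block influence it? |
|---|---|---|
| Unable to score pain on the NRS | Screening | No |
| Conversion to open surgery | During surgery, before the block | No |
| PCA item, read as inability to use the device | Screening | No |
| PCA item, read as a device fault | After randomisation and block | Not obviously |
| QoR-15 item, preoperative form | Before the block | No |
| QoR-15 item, 24-hour form | After randomisation and block | Yes, through recovery |

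**When removal biases the comparison**

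Let f be the share of an arm removed and g the mean difference between removed and retained patients. The full-arm mean is (1 − f) × retained mean + f × (retained mean + g) = retained mean + f × g. The retained mean therefore differs from the full-arm mean by −f × g. The between-arm difference is displaced by −(f₁g₁ − f₂g₂).

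- If removal works the same way in both arms, f and g have the same expected values in each, the displacement cancels in expectation, and the retained comparison is not biased. This is so even if the removed patients did worse than the rest.
- If f or g depends on arm, directly or through an outcome that the blocks affect, the displacement does not cancel. The documents give neither quantity, so no size can be attached to this case.

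**Precision cost when removal does not depend on arm**

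Inputs: arms of 35 and 37 (Study Protocol). Assumptions: these are the numbers left after removal, the SD is common and unchanged, and one or three patients were removed.

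- As stated: SE = SD × √(1/35 + 1/37) = 0.2358 SD.
- One patient restored: √(1/36 + 1/37) = 0.2341 or √(1/35 + 1/38) = 0.2343. Ratios: 0.2358/0.2341 = 1.007 and 0.2358/0.2343 = 1.006, so the SE is about 0.7% larger because of the removal.
- Three patients restored: from √(1/38 + 1/37) = 0.2310 to √(1/35 + 1/40) = 0.2315, depending on arm. Ratios: 1.021 and 1.019, so the SE is about 2% larger.

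**The case against.** **The PCA item may be a screening criterion.** Its wording concerns patients using the device, and the NRS item in the same list is an ability criterion. On that reading it does no harm. This stands as a possibility. But the list describes inability explicitly for NRS and QoR-15 and words the PCA item differently, and it includes conversion to open surgery, which cannot be known at screening. The text leaves the matter open.

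**No patient is shown to have been removed.** This stands in full. The 72 can be read as everyone included and assigned. A reader might take the 35/37 split as a sign of removals, but a difference of two patients is ordinary under simple 1:1 allocation and is not evidence either way.

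**Arm-dependent removal is unlikely.** Both arms have the same PCA protocol, and postoperative follow-up is blinded. This largely answers the worry about device faults. It answers less for 24-hour QoR-15 non-completion, which can follow from recovery itself.

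Two stronger readings are tempting and should be resisted:

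- *A PCA fault affects only tramadol data.* With on-demand boluses and no background infusion, a delivery fault interrupts PCA analgesia and may change pain scores, rescue use, PONV and QoR-15. The supportable statement is narrower: only tramadol consumption becomes unmeasurable, and the other outcomes are still observed.
- *Losing a few patients with poor outcomes, by chance mostly from one arm, inflates the false-positive rate.* If the removal mechanism is the same in both arms, the retained patients have the same distribution in each when the blocks do not differ, however unevenly the removals happen to fall. Inflation requires a mechanism that depends on arm.

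**Conclusion.** The point holds as a defect in the plan, not as a demonstrated bias. Two patient-level exclusions lack a time point. On the natural reading of one, and on one of two readings of the other, they remove patients after randomisation and block, and nothing in Statistical Methods limits this.

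If removal does not depend on arm, the consequence is a small loss of precision: about 0.7% on the standard error for one removal and about 2% for three, both counts being assumptions. Bias would require removal that depends on arm, which the documents neither show nor exclude. The 24-hour QoR-15 item is the more serious of the two, because non-completion may reflect poor recovery. If neither rule was ever applied after randomisation, a sentence saying so settles whether any bias arose.

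Confidence is medium, because the meaning of the PCA item is uncertain and the number of exclusions is not given. It should be fixed because the remedy is cheap and better than the rule as written.

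**What to change.** The study has been conducted, so the change applies to the analysis and the report:

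1. Analyse every randomised patient with collected data in the assigned arm.
2. Read the PCA and QoR-15 exclusions as inability identified before randomisation, and say so.
3. Treat a PCA fault as missing tramadol data from the fault onward, keeping intervals completed before it. Treat an incomplete 24-hour form as missing QoR-15 only.
4. Keep all other recorded outcomes, flagging those recorded after a PCA delivery fault.
5. Report, per arm, the numbers randomised, excluded with reason (including conversions to open surgery) and analysed, or state that none were excluded.

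A sensitivity analysis giving the worst rank to patients who did not complete the 24-hour QoR-15 is optional. It would not suit device faults, which say nothing in themselves about recovery.

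The cost is some wording and one flow table, with no extra patients or staff. The downsides are a few missing values to handle, outcomes after a delivery fault that reflect interrupted PCA, and the limit that excluded patients can be restored only where their data were collected.

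### Patients appear to be randomised before surgery although the arms differ only after it, so some can be lost in between, and nothing stated ensures that remifentanil is titrated blind to arm

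*Combined protocol and SAP*

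**What the plan says.** All references are to the combined protocol and SAP.

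- **Randomisation.** The opening of the Study Protocol says: "Patient randomization was performed using an internet-based software program". It gives no time of randomisation, no method of concealment and no moment at which allocation is disclosed.
- **Order of events.** The paragraph on consent and anaesthesia begins: "All necessary information regarding the procedures was provided to the randomized patients, and their written consent was obtained". The baseline questionnaire follows: "Preoperative QoR-15 questionnaires were completed before patients were taken to the operating room". Monitoring, induction and surgery come after that.
- **Time of treatment.** The paragraph on the block procedures says: "After the completion of the surgery, all block procedures were performed under sterile conditions while the patient was supine under anesthesia".
- **Exclusions that can arise in theatre.** The Exclusion criteria list includes "Patients where laparoscopic surgery was converted to open surgery" and "Patients undergoing a second procedure along with laparoscopic cholecystectomy".
- **Blinding.** "Surgeons and postoperative follow-up healthcare workers were not informed of the group assignments". The later paragraph on ward follow-up adds that the anaesthetist assessing postoperative pain is blinded. The anaesthetist in theatre is mentioned in neither place.
- **Intraoperative opioid.** "The remifentanil infusion was adjusted in the range of 0.01-0.2 mcg/kg/min", with the aim of holding mean arterial pressure within 20% of baseline. The recorded items in this part of the protocol are mostly times (induction, surgery, anaesthesia, block). Remifentanil dose is not among them.
- **Group sizes.** The 72 patients are 35 in Group 1 and 37 in Group 2, and each group is described by the block its members received.

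**The concern.** Both arms have the same care until the operation is over. Nothing in the design requires allocation to be made, or known, before then. Placing it earlier opens two gaps.

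First, a patient converted to open surgery becomes ineligible after randomisation and before treatment. The same may be true of a patient who has a second procedure decided in theatre. The Statistical Methods section defines no analysis population and no rule for patients excluded after randomisation, and there is no separate count of patients randomised. A reader cannot follow the numbers from randomised to analysed.

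Second, if the theatre anaesthetist can learn the arm before surgery ends, opioid titration during surgery is not guaranteed to be independent of it. Fentanyl at induction, paracetamol and tramadol are given at set doses. Remifentanil is the intraoperative analgesic left to adjustment. The outcomes nearest in time are the pain scores at 0 and 1 hour, tramadol in the first hour and rescue fentanyl in the recovery room. With no dose listed as recorded, the planned data would not allow a check for imbalance.

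**Working it through.** The plan has no sample-size calculation, dropout allowance or conversion rate, so there is no figure of its own to reproduce beyond the group sizes: 35 + 37 = 72, which agrees.

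**1. Sequence.** Reading the Study Protocol in order gives: patients called randomised, informed and consented; baseline QoR-15; theatre and induction; remifentanil titration and surgery; end of surgery; block. Conversion can occur only during surgery, so it falls after randomisation and before treatment. A second procedure may be planned beforehand or decided in theatre; the criterion does not say which.

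Randomisation before surgery is an inference from this order. The opening paragraph says patients were included after consent, while the later paragraph describes consent from patients already randomised. The narrative is therefore not a strict timetable.

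**2. What 72 counts.** Both groups are described by the block received. Either all randomised patients reached their block and none was lost beforehand, or some were lost and are not among the 72. On both readings, losses before the block do not reduce the 72; they add to the number randomised.

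**3. Size of the loss, under assumed rates.** To leave 72 after a fraction L is lost, randomise 72 / (1 − L), rounded up:

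| Assumed L | 72 / (1 − L) | To randomise | Extra patients |
|---|---|---|---|
| 3% | 74.2 | 75 | 3 |
| 5% | 75.8 | 76 | 4 |
| 10% | 80.0 | 80 | 8 |
| 15% | 84.7 | 85 | 13 |

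As an outer bound, set the group descriptions aside and suppose that 72 was the number randomised. With 35 against 37, two-sided alpha of 0.05 (sidedness is not stated) and a normal approximation, 80% power corresponds to a standardised difference of (1.960 + 0.842) × √(1/35 + 1/37) = 0.66. Shrinking both groups by L gives power Φ(2.802 × √(1 − L) − 1.960): 79% at L = 3%, 78% at 5%, 76% at 10% and 73% at 15%.

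**4. Does the 35/37 split show loss?** Under simple 1:1 randomisation of 72, the only more even split is 36/36. The chance of a split at least as uneven as 35/37 is 1 − C(72,36)/2^72 = 0.91. The split is no evidence of loss.

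**5. The theatre anaesthetist.** The roles named as blinded are surgeons, postoperative staff and the pain assessor. No text says that the theatre anaesthetist was told the arm, and none says that this person was not. The permitted remifentanil range is 0.2 / 0.01 = 20-fold. That is the span of allowed infusion rates, not a difference between arms, and nothing in the documents allows an arm difference to be estimated.

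**The case against.** The strongest reply is that this is a reporting gap and not a shown flaw. No time of randomisation is given, and a list generated early but opened at the block would fit the text. The theatre anaesthetist's knowledge of the arm rests on silence. Titration is tied to a blood-pressure target, both arms receive an active block, and there is no obvious direction in which knowing the arm would shift the dose. Conversion is decided by surgeons who do not know the arm, before treatment differs, so it cannot favour either block. The trial is written up in the past tense with dates from January to May 2024, so its allocation procedure can no longer be changed.

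Most of this stands, and it rules out several stronger readings that a reader might infer:

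- That the theatre anaesthetist knew the arm and dosed accordingly. The documents permit this but do not show it.
- That the 20-fold range measures a possible bias. It measures the limits of titration.
- That some of the 72 were lost before a block. The groups are described by block received.
- That conversions bias the comparison. With blinded surgeons and no treatment difference yet, they do not do so directly.

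Two things remain. Conversion is an explicit intraoperative exclusion with no handling rule. And a trial that calls itself blinded does not say when allocation was opened or whether the person adjusting the opioid knew it. A pressure target narrows discretion without removing it.

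**Conclusion.** The concern holds in a limited form. On the order of events that the protocol implies, the operation lies between randomisation and treatment, and patients can be excluded in that interval. The cost is patients and clear accounting: about 3 to 4 more to randomise at an assumed loss of 3% to 5%. It is not direct bias. Arm-dependent remifentanil titration is possible because neither concealment until the block nor blinding of the theatre anaesthetist is stated. It is not shown, and no size can be attached to it. The conclusion rests on reading the protocol's order as the order of events, and on allocation having been available to theatre staff before the block. If allocation was in fact opened only at the block, titration was blind to arm, and any loss before the block was unrelated to arm. A moderate rating is fair: it should be put right because a better procedure is simple, but it does not by itself undermine the comparison.

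**What to change.** For this design: confirm preoperative eligibility and obtain consent before surgery, then open a sealed sequential allocation only once surgery has ended laparoscopically with no second procedure, immediately before the block. Conversions and second procedures then become ineligibility before allocation is opened, and the intraoperative phase is managed without knowledge of the arm. Record total remifentanil for each patient and report it by arm. With sealed envelopes this needs no extra staff, visits or patients, and it changes no dose or clinical rule. The small cost is that the block set-up is known a few minutes later. It does not deal with the exclusion for technical problems with PCA devices, which arises after the block and still needs a rule of its own.

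If the trial is already complete, report when allocation was generated and when it was opened, whether the theatre anaesthetist and the block operator knew it, and the numbers randomised and excluded by arm with reasons. Define the analysis population, clarify the order of consent and randomisation, and give remifentanil dose by arm if the anaesthesia charts hold it. This costs only a search of existing records and a few lines of text.

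### Does leaving recovery-room fentanyl rescue out of the tramadol totals make the comparison of the two blocks misleading?

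*Combined protocol and SAP*

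**What the plan says.** The Study Protocol's account of postoperative analgesia sets the device as follows: "The PCA protocol was set to 10 mg bolus tramadol on demand with a 20-minute lockout period without basal infusion". The consumption measure is then given by drug and window: "Tramadol consumption was recorded at 0-1 hour, 0-12 hours, 12-24 hours, and the total at 24 hours". The next sentence covers a second opioid: "Patients with a pain score above 4 in the recovery room received 25 mcg iv fentanyl as rescue analgesia, which was recorded". Stay in the recovery room ends on a clinical score and not at a fixed time: "Patients with an Aldrete score of 9 or higher were transferred to the ward".

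Later rescue is a non-opioid: "Patients with pain scores above 4 despite the analgesic regimen received 50 mg iv dexketoprofen". The text does not say that its use was recorded, whereas for the antiemetic it does: "The total ondansetron dose administered within the first 24 hours postoperatively was recorded". Every patient also had "1 mg/kg tramadol (Tramosel, Haver farma ilaç, Turkey" before the end of surgery.

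Statistical Methods assigns tests by type of data and names no outcome. Continuous variables are compared by t-test or Mann-Whitney U. Categorical variables are shown as counts and percentages, and "Relationships between categorical variables for two independent groups were evaluated using the Chi-square test or Fisher exact test".

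**The concern.** The trial compares two blocks, and the need for analgesia is a direct reading of how well a block works. Two opioids are given after surgery, but only one is summed. Fentanyl goes to patients in pain, so it is part of the response to the block and not background noise.

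The first hour looks most exposed. The lockout caps PCA tramadol at about 30 mg, so a patient who needs more cannot show it in tramadol, and rescue is where the extra need would appear. If the arm that uses more PCA also gets more rescue, tramadol alone understates the difference. If the other arm gets more rescue, it overstates the difference and could even reverse its sign. A reader might then be misled about which block spared more opioid.

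**Working it through.** The documents give no rescue rates, no conversion between the two opioids, and no tramadol mean or SD. There is therefore no stated figure to reproduce, and the sizes below are conditional on assumptions.

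**Inputs from the Study Protocol:** 10 mg bolus, 20-minute lockout, no basal rate; 25 mcg fentanyl per rescue; 35 and 37 patients.

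**Assumptions:** one 25 mcg dose per rescued patient; each dose worth 10 to 40 mg of iv tramadol; a gap between arms of up to 20 percentage points in the proportion rescued, in either direction.

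**1. PCA ceiling** = bolus × window ÷ lockout.
- 0-1 h: 10 × 60/20 = 30 mg (40 mg if boluses at minute 0 and minute 60 both count).
- 24 h: 10 × 1440/20 = 720 mg.

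**2. Shift in the mean difference if fentanyl were counted** = (gap in doses per patient) × (mg tramadol per dose).
- Gap ±0.10: ±1 mg at factor 10, ±2.5 mg at 25, ±4 mg at 40.
- Gap ±0.20: ±2, ±5 and ±8 mg.
- Gap 0: no shift.

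The largest shift, 8 mg, is 8/30 = 27% of the first-hour ceiling and 8/720 = 1.1% of the 24-hour ceiling. Ceilings are not average use, so these ratios only give scale.

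**3. Can the sign change?** The sign reverses when the factor exceeds (tramadol difference) ÷ (opposing gap in doses).
- Tramadol difference 5 mg, opposing gap 0.20: break-even 5/0.20 = 25 mg, inside the assumed range. The total runs from 5 − 2 = 3 mg to 5 − 8 = −3 mg.
- Tramadol difference 5 mg, opposing gap 0.10: break-even 50 mg, outside the range.
- Tramadol difference 10 mg, opposing gap 0.20: break-even 50 mg, outside the range.

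So within these assumptions a reversal needs a tramadol difference below 40 × 0.20 = 8 mg, less than one bolus per patient, together with a large rescue gap the opposite way.

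**4. Do the existing rules reach the rescue data?** Fentanyl given or not is a categorical variable in two independent groups, so it gets counts, percentages and chi-square or Fisher. Fentanyl dose is a numerical variable, so it gets the t-test or Mann-Whitney U. Nothing further has to be collected.

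**5. How precise would that comparison be?** Newcombe 95% intervals for the difference in proportions, with illustrative counts out of 35 and 37:
- 4 vs 4: +0.6 points (−14.9 to 16.5)
- 7 vs 11: −9.7 points (−28.6 to 10.3)
- 11 vs 7: +12.5 points (−7.5 to 31.6)
- 18 vs 18: +2.8 points (−19.4 to 24.5)

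A non-significant test would not show equal rescue. That argues for giving an interval in the report, but it does not show an error in the plan.

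**6. The intraoperative tramadol dose.** It was given before surgery ended, so windows starting at 0 hours postoperatively read naturally as PCA. Were it included, it is the same weight-based dose in both arms, and randomisation balances it on average. It would add spread from body weight, but no expected difference between the arms.

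**The case for a change.** The strongest case for a change is this. General tests do not commit anyone to report rescue, and no test supplies a rule for combining two opioids. Pain scores do not fill the gap either, because scores taken after rescue are lowered by it. Reporting rescue by arm costs one table row and needs no conversion factor, and a converted total could sit beside it with a sensitivity range.

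Much of this stands. No section combines the opioids, the first-hour cap is real, and pain scores are best read with rescue beside them. But three points limit it.

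- The absence of a named comparison is not peculiar to fentanyl. Statistical Methods names no outcome, so the same can be said of tramadol, pain scores, the recovery questionnaire and nausea. It is a feature of the whole section, not a separate fault in the handling of rescue.
- The plan never presents tramadol as total opioid. Fentanyl is not left out of a measure that claims to contain it; it is recorded as a variable of its own.
- A converted total is a new endpoint with costs. Its factor would come from outside the documents, and it can be noisier than tramadol alone if rescue is only loosely tied to PCA need. Since recovery-room time need not match 0-1 h, placing fentanyl in that window could misassign it.

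The silence on whether dexketoprofen use was recorded is a missing detail of the same kind. It is settled by reporting what was charted.

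**Conclusion.** No change to the plan follows. The text leaves detail unstated, and analysts would fill it sensibly: fentanyl rescue by arm, as number, percentage and dose, falls under the tests already listed, and an interval for the difference would be a useful courtesy to readers. Whether to add an opioid-equivalent total is a judgement on which reasonable statisticians differ, and separate reporting of the two drugs is a fair choice.

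No bias of known direction or size is shown. Under the assumptions of 10 to 40 mg tramadol per fentanyl dose, one dose per rescued patient and a rescue gap within 20 points, the mean difference moves by between −8 and +8 mg. The sign can change only when the tramadol difference is below 8 mg and rescue runs the other way. More doses per patient, a wider gap or a larger factor would raise these limits in proportion. The conclusion rests on the recorded fentanyl data being reported beside the tramadol results. If a report claimed total opioid sparing from tramadol alone, that would be a fault of the report and not of this plan.
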